### **6.6 RESCUE THERAPY**

During the course of the study, for patients requiring rescue therapy as per the judgement of the study physician, additional medications may be utilized. The benefit/risk of using additional medications in combination with study medication should be carefully considered. It is recommended that site-specific rescue therapy be identified and reserved for use prior to randomization. Administer rescue medication only 48 hours after the last infusion of study medication.

Rescue medications are defined as the immunosuppressive therapies (described in the exclusion criteria [E 03](#) and [E 04](#)).

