2.4.4.1 Analysis of primary efficacy endpoint(s)

The primary efficacy analysis will be pairwise comparisons between sarilumab doses (400 mg and 200 mg) and placebo with respect to the primary endpoint, time to improvement of 2 points in clinical status assessment from baseline using the 7-point ordinal scale, using a log-rank test stratified by randomization stratum with treatment as a fixed factor in the mITT population. P-values for the pairwise comparison of each sarilumab dose versus placebo will be provided.

Hazard ratios for the estimation of treatment effect of each sarilumab dose compared to placebo will be provided using Cox proportional hazards model stratified by the randomization stratum with treatment as a covariate, along with 2-sided confidence intervals. Kaplan-Meier (KM) plot and the median time-to-improvement of 2 points will also be provided by treatment groups.

Superiority of sarilumab over placebo will be declared if the null hypothesis is rejected at the 5% (2-sided) significance level following the multiplicity control procedure specified in [Section 2.4.4.3](#).

Patients who have an improvement of 2-points in clinical assessment or discharge (other than death) will be considered as events, while patients who do not experience improvement of 2-points will be censored at the last observation time point. Patients who take rescue medication in the study without improvement of 2-points before that will be censored at the date of rescue medication started.

In addition, the proportion of patients with at least 2-point improvement from baseline at each day post-baseline will be provided using descriptive statistics. Graphical presentations (bar charts) will be used to examine trends over time.

The analyses using the log-rank test and Cox PH model specified above will be repeated for the severe patients and critical patients at baseline as recorded on CRFs.

Baseline clinical status is defined as the worse (lower) value of screening visit and Day 1 prior to dosing. If there is a tie, flag Day 1 as baseline. Baseline values are 2, 3, 4, 5, or 6. Values 1 and 7 do not apply (if 1 or 7 appear, then data query is needed.)

Post-baseline clinical status values range from 1 through 7 on ordinal scale and data will be as recorded on the ordinal scale eCRF.

Handling of death or discharge on clinical status assessment (post-baseline)

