Changes from baseline in the 7-point ordinal scale for Day 4, 7, 15, 21, 29 (or until discharge) will be analyzed using an ANCOVA model with treatment group and randomization strata as fixed effects and baseline value as a covariate. The least squares (LS) treatment mean difference from placebo with standard error, along with corresponding 95 % confidence interval and p-value will be provided. Graphical presentations (line plot with mean and error bar) will also be used to examine trends over time using mean values (\pm SE) and mean changes from baseline (\pm SE).

The 7-point ordinal scale at each day and their changes from baseline will also be summarized for each treatment group through descriptive statistics including mean, median, standard deviation, minimum and maximum.

Fever

Body temperature is collected using varying methods (the routes in eCRF are axillary, auricular, oral, rectal) at multiple timepoints each day.

Baseline body temperature is defined as the highest temperature at any time prior to first dose.

Post-baseline body temperature is defined as the highest temperature from each day among all temperatures from different timepoints (morning, evening, etc).

Patients body temperature and its change from baseline will be summarized at each day by treatment group by timepoint over the study period. Graphical presentations (line plot with mean and error bar) will also be used to examine trends over time using mean values (\pm SE) and mean changes from baseline (\pm SE).

All temperatures will be converted to oral values as following:

- Rectal/Auricular subtract 0.6 deg C = Oral deg C
- Axillary add 0.6 deg C = Oral deg C

Analysis of endpoint #3: time to resolution of fever

Resolution of fever is defined as body temperature ($\leq 36.6^{\circ}\text{C}$ [axilla], or $\leq 37.2^{\circ}\text{C}$ [oral], or $\leq 37.8^{\circ}\text{C}$ [rectal or auricular]) for at least 2 consecutive days without antipyretics or until discharge, whichever is sooner.

The analysis will be performed similarly to the primary endpoint.

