Patients who achieved resolution of fever or discharge (other than death) will be considered as events, while patients who do not experience resolution of fever will be censored at the end of study. Patients who started rescue therapy or died in the study will not be considered as having an endpoint event and will be censored at the earlier date of death or rescue therapy start date. Patients who do not have fever at baseline will be censored at the first dose date.

Analysis of endpoint #5: the number of days with fever

Fever is defined as body temperature $>37.4^{\circ}\text{C}$ (axillary), or $>38^{\circ}\text{C}$ (oral), or $>38.4^{\circ}\text{C}$ (rectal or auricular).

The number of days with fever will be analyzed using the ANCOVA model with treatment group and randomization strata as fixed effects for patients alive by Day 29. The LS treatment mean difference from placebo with standard error, along with corresponding 95 % confidence interval and p-value will be provided.

Summary statistics with mean, median, standard deviation, minimum and maximum will be provided. Histogram will be provided to illustrate the distribution of days with fever.

In addition, the percent of days with fever ($100 \times$ number of days with fever divided by number of days of follow-up, defined as the earlier date of death or discharge or last visit up to Day 29) for all patients, will be analyzed using the ANCOVA model with treatment group and randomization strata as fixed effects.

Improvement in Oxygenation

Improvement in oxygenation is defined as increasing in SpO₂/FiO₂ of 50 or greater compared to the nadir SpO₂/FiO₂. Nadir SpO₂/FiO₂ is the nadir (lowest value) at any point in the study, and looking forward, an improvement in oxygenation is increase of 50 or greater from nadir value for at least 48 hours. If nadir is observed on 2 or more different days post baseline, the day of the first occurrence of nadir will be used.

Baseline SpO₂/FiO₂ ratio is defined as the last available ratio prior to first dose.

Post-Baseline SpO₂/FiO₂ ratio is defined as the worst (minimum) value in each day.

For derivation of FiO₂, please see conversion table in [Section 2.5.2](#).

***Analyses of endpoint #4: time to resolution of fever and improvement in oxygenation,
#9: time to improvement in oxygenation, and
#14: time to saturation $\geq 94\%$ on room air***

The analysis of these endpoints will be performed similarly to the primary endpoint.

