Patients who do not experience the event under analysis will be censored at the last observation time point. Patients who die or take rescue medication in the study without experiencing the event will be censored at the earlier date of death or rescue medication started.

***Analyses of endpoint #11: days of hypoxemia,
#12: days with supplemental oxygen use,
#13: days of resting respiratory rate >24 breaths/min, and
#15: ventilator free days in the first 28 days***

The analysis of these endpoints will be performed using the ANCOVA model with treatment group and randomization strata as fixed effects for patients alive by Day 29. The LS treatment mean difference from placebo with standard error, along with corresponding 95 % confidence interval and p-value will be provided. Patient discharged early will be considered as ventilator free until the next hospitalization (if applicable).

Summary statistics with mean, median, standard deviation, minimum and maximum will be provided. Histogram will be provided to illustrate the distribution.

In addition, the percent of days with each endpoint ($100 \times$ number of days with the endpoint divided by number of days of follow up, defined as the earlier date of death or discharge or last

visit up to Day 29) for all patients, will be analyzed using the ANCOVA model with treatment group and randomization strata as fixed effects.

Analyses of endpoint #10: % of patients alive off oxygenation at Day 29, and #16: % of patients with initiation of mechanical ventilation, non-invasive ventilation, or use of high flow nasal cannula, and

These endpoints will be analyzed using a Cochran-Mantel-Haenszel (CMH) test stratified by randomization strata. The difference in proportions of patients for each Sarilumab dose compared to placebo (sarilumab - placebo), along with associated 2-sided 95% confidence levels, and p-value will be provided.

Bar plots will also be provided to illustrate the difference among treatments.

NEWS2

Please find NEWS2 score calculation and details in [Section 2.5.2](#).

Analyses of endpoint #6: Time to change in National Early Warning Score 2 (NEWS2) from baseline, and #7: Time to NEWS2 of <2 and maintained for 24 hours

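### Endpoint #3 (time to resolution of fever): read literally, the SAP's rescue/death rule removes resolutions that preceded rescue or death, in conflict with the SAP's own neighbouring rules

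*SAP*

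**What the plan says.** SAP section 2.4.4.2 defines resolution as temperature at or below the route-specific limit "for at least 2 consecutive days without antipyretics or until discharge, whichever is sooner". It then says of the method: "The analysis will be performed similarly to the primary endpoint". Two sentences govern event status for endpoint #3:

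- Event rule: "Patients who achieved resolution of fever or discharge (other than death) will be considered as events".
- Rescue/death rule: "Patients who started rescue therapy or died in the study will not be considered as having an endpoint event and will be censored". The date is given in the same sentence: "censored at the earlier date of death or rescue therapy start date".

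The comparable rules elsewhere in the SAP are worded differently:

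- Primary endpoint (2.4.4.1): "Patients who take rescue medication in the study without improvement of 2-points before that will be censored at the date of rescue medication started". This sentence covers rescue only, not death.
- Endpoints #4, #9 and #14 (2.4.4.2), with the same wording for #7: "Patients who die or take rescue medication in the study without experiencing the event will be censored at the earlier date of death" or rescue start.
- All time-to-event endpoints (2.4.4, below Table 3): the event is dated at its first occurrence.

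Protocol section 9.4.3.1 plans Kaplan-Meier estimates with confidence intervals for the other time-to-event secondary endpoints. It gives no censoring rule for #3.

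**The concern.** Every comparable rule restricts rescue (and, for #4, #7, #9 and #14, death) censoring to patients who have not yet had the event. The #3 sentence alone lacks that restriction. Its statement that such patients have no endpoint event adds nothing for a patient who never resolved, who is already a non-event. It changes status only for a patient who would otherwise count. It may have been meant for resolution after rescue, but it does not say so.

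Followed as written, it makes event status on Day 3 depend on what happens on Day 12 or Day 25, and it keeps the patient in the risk set as unresolved until then. It also gives an impossible ordering. A patient with fever resolved and oxygenation improved by Day 5 who dies on Day 20 is an event for #4 (both) but not for #3 (fever alone). A death between the Day 29 and Day 60 analyses could likewise remove a resolution counted at Day 29.

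What is at stake is the log-rank p-value, hazard ratio and curves for #3. Two programmers could derive different results from the same data.

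**Working it through.** **1. The plan's own figure.** The documents give no power or event rate for #3. The only power statement concerns the primary endpoint (SAP 1.3): at least 90% for about 160 versus 80 patients, with 45% versus 70% improved at Day 15, two-sided 0.05. It reproduces:

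- Exponential hazard ratio = ln(1 − 0.70)/ln(1 − 0.45) = 2.01.
- Events by Day 15 = 160 × 0.70 + 80 × 0.45 = 148.
- Schoenfeld: z = ln(2.01) × √(148 × 1/3 × 2/3) − 1.96 ≈ 2.06, power 98%.

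That figure is not affected by the present point.

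**2. The two readings.** Let T be the day of resolution or discharge, R the earlier of rescue and death, and C the end of follow-up.

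- Qualified rule (as for #4, #7, #9, #14): event if T precedes R and T ≤ C; time = min(T, R, C).
- Literal rule: if R ≤ C, non-event with time R, whatever T was. Otherwise event if T ≤ C, with time min(T, C).

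They differ only for patients with T before R ≤ C. Such patients can exist, because rescue is possible after an early resolution (Protocol 6.6: "Administer rescue medication only 48 hours after the last infusion of study medication").

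**3. Simulation inputs, all assumed except the test and the planned arm sizes.** Daily times to Day 29, rescue/death independent of fever, no separate discharge process, two-sided 0.05.

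- Set A: 160 versus 80, all febrile at baseline; placebo median 3 or 5 days; no fever effect, or a daily hazard ratio of 1.5.
- Set B: 80 versus 40 (half the planned arms febrile); rescue/death from Day 3; medians 3 versus 5 days (5/3 = 1.67), or 4 days in both arms for no effect.

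**4. Equal rescue/death in both arms, real fever effect: dilution**

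| Set | Rescue/death per arm | HR qualified → literal | Power qualified → literal |
|---|---|---|---|
| B | 10% | 1.67 → 1.42 | 70% → 37% |
| B | 20% | 1.67 → 1.31 | 70% → 21% |
| B | 30% | 1.67 → 1.22 | 70% → 12% |
| A | 10% | 1.42–1.44 → 1.23–1.29 | 74–75% → 29–43% |
| A | 20% | 1.42–1.45 → 1.17–1.23 | 73–78% → 15–25% |

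In Set A with equal 20% and no effect, 0.20 × 240 = 48 patients are rescued or dead. Of these, 37–41 had already resolved, so events fall from 225–233 to 188–192 (about 16–18% lost). The Kaplan-Meier proportion resolved by Day 7 falls from 80% to 66% (median 3 days) or from 62% to 51% (median 5 days). The hazard ratio stays at 1.00–1.01 and rejection at 3–4%, so no false effect arises.

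**5. Unequal rescue/death, no fever effect: spurious effect under the literal rule**

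| Set | Sarilumab vs placebo | HR | Rejection |
|---|---|---|---|
| B | 15% vs 20% | about 1.1 | 4–7% |
| A | 15% vs 20% | 1.10–1.11 | 7–9% |
| B | 10% vs 20% | 1.24 | 17% |
| A | 20% vs 30% | 1.20–1.23 | 20–27% |
| B | 15% vs 30% | 1.38 | 30% |
| A | 15% vs 30% | 1.31–1.37 | 41–50% |

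A repeat of Set B with rescue/death uniform over Days 3–29 gave 20% and 35% for the 10% vs 20% and 15% vs 30% rows. Under the qualified rule the hazard ratio is about 1.0 and rejection no more than about 5% throughout.

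**6. Sensitivity to independence.** If the hazard of rescue/death after resolution is one quarter of that before it, the Set B rates of 17% and 30% become about 9% and 19%. The dilution largely remains: at 20% in both arms the hazard ratio still falls from about 1.66 to 1.28.

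**The case against.** The strongest reply is that the literal reading was not intended. The preceding sentence makes resolution or discharge an event, the SAP points #3 to the primary analysis, and the general rule dates an event at its first occurrence. The illogical ordering of #3 and #4 supports the same view. This stands as far as intent goes: a reader might infer that the SAP definitely cancels earlier resolutions, and the documents do not settle that. They contradict themselves, probably through an omitted qualifier. But the rescue/death sentence is the specific rule and the other two are general, so the conflict has to be removed.

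A reader might also infer that the #3 result would be driven by rescue and death instead of fever. That is not supported. In Set A, about 76–92% of events are kept even under the literal rule, and all are true resolutions. Nor does the rule create a false effect by itself. That needs an imbalance in rescue or death, and the documents give no such rates. Rescue use (#17) and Day 29 survival are, however, outcomes on which the trial looks for a difference.

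Two further limits stand. The listed concomitant medications, including rescue, are captured only until discharge (Protocol 6.5, SAP 2.1.2), so after discharge mainly death could remove an event; the simulations do not model this. And #3 is one of 19 other secondary endpoints outside the testing hierarchy (SAP 2.4.4.3), so its p-value is nominal.

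**Conclusion.** The #3 rescue/death sentence is wrong as written: it conflicts with four other statements in the SAP (the event rule, the link to the primary analysis, first-occurrence dating, and the no-prior-event qualifier used for the other endpoints). Followed literally, it conditions the endpoint on the future.

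The size is conditional on that reading and on assumed rates. Equal rescue/death of 10–30% per arm takes a hazard ratio of about 1.67 to about 1.4–1.2, with a large loss of power. With no fever effect, a mild imbalance (15% versus 20%) leaves rejection near nominal at about 4–9%. Imbalances from 10% versus 20% to 15% versus 30% give about 17–50%, depending on sample size and assumptions, and less if rescue or death is rarer after resolution. The possible drift between Day 29 and Day 60 was not quantified.

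The consequence is confined to #3. The primary and key secondary analyses, and the primary power statement, do not change. The correction should be made, but no confirmatory claim depends on it.

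**What to change.** In SAP section 2.4.4.2, endpoint #3, insert *without prior resolution of fever or discharge* into the rescue/death sentence. State that patients whose fever resolved, or who were discharged, before rescue or death remain events on that date. This brings #3 into line with #4, #7, #9 and #14, and with the primary endpoint for rescue. The primary endpoint sentence in the SAP is not a template for deaths, because it does not mention them. The censoring date for patients who never resolve is a separate matter and need not change here.

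The cost is one phrase in the SAP and the matching line in the programming specification, before the primary database lock. No new data are needed.

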### Medical conditions and prior/concomitant therapy

#### E 01. In the opinion of the investigator, unlikely to survive after 48 hours, or unlikely to remain at the investigational site beyond 48 hours.

Note: Multi-organ dysfunction patients (defined as dysfunction of 2 or more organ systems) and patients requiring extracorporeal life support or renal replacement therapy are excluded.

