2.4.4 Analyses of efficacy endpoints

Table 3 below summarizes the analyses for each type of efficacy endpoints in general.

Table 3 – Summary of analyses for each type of efficacy endpoint

Type of endpoint	Statistical method	Graphical presentation
Time-to-event	Log-rank test (stratified) Cox-PH model (stratified)	KM curve
% of patients over time	CMH test (stratified) Descriptive statistics	Bar plot over time
% of patients at end	CMH test (stratified) Descriptive statistics	Bar plot
Continuous variable over time	ANCOVA model Descriptive statistics	Line plot over time
Continuous variable at end	ANCOVA model Descriptive statistics	Histogram

For time to event analysis, the time to event duration is calculated as:

$$\text{Date of first occurrence/episode of the event} - \text{date of first dose} + 1.$$

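### Endpoint #3 (time to resolution of fever): censoring patients without baseline fever on Day 1 can make the Kaplan-Meier percentages resolved too low, if any resolution is dated Day 1

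*SAP*

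**What the plan says.** SAP 2.4.4.2 analyses endpoint #3 in the same way as the primary endpoint: stratified log-rank test, stratified Cox model, Kaplan-Meier curve and median (SAP 2.4.4.1). The population is mITT (SAP 2.3.1.1), not the febrile patients only. For patients without fever at the start the rule is: "Patients who do not have fever at baseline will be censored at the first dose date".

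Four other SAP statements bear on this:

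- **Time scale (2.4.4).** Time runs from the "Date of first occurrence/episode of the event", minus the date of first dose, plus 1.
- **Event (2.4.4.2).** Temperature must be at or below the resolution threshold "for at least 2 consecutive days without antipyretics or until discharge, whichever is sooner". Discharge also counts: "Patients who achieved resolution of fever or discharge (other than death) will be considered as events".
- **Baseline (2.4.4.2).** "Baseline body temperature is defined as the highest temperature at any time prior to first dose".
- **After baseline (2.4.4.2).** Each day is represented by its highest reading.

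The SAP does not say whether the two-day run is dated at its first or its second day. It also does not say whether the Day 1 maximum includes readings taken before the dose.

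**The concern.** A patient without fever at baseline cannot have the event, yet by the time formula is censored at time 1. By the usual convention, patients censored at a given time are still at risk for events at that time. These patients therefore sit in the denominator for any Day 1 event and leave straight after it.

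If some febrile patients have an event on Day 1, the first step of the curve is diluted and the later curve starts from too high a level. The percentages resolved and the median would then describe neither the febrile patients nor the whole mITT population. The first days are of particular interest here. Protocol 2.2 cites a retrospective series of 21 patients treated with another IL-6 receptor blocker, in which all had normal temperature one day after treatment.

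**Working it through.** The plan states no figure for this endpoint, so there is none to reproduce.

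**Step 1. Time assigned to afebrile patients.** First dose date − first dose date + 1 = 1. They are at risk on Day 1 and on no later day.

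**Step 2. Can an event be dated Day 1?**

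- Run dated at its first day: yes. Screening can be on Day −1, and readings from the previous 24 hours can be used for screening (Protocol 1.3). A patient febrile only on the day before dosing, and below the threshold on Days 1 and 2 without antipyretics, has an event at time 1. This holds even if the Day 1 maximum includes pre-dose readings.
- Run dated at completion: no. The earliest resolution is Day 2. A Day 1 discharge would still count, but exclusion E 01 (Protocol 5.2) keeps out patients judged "unlikely to remain at the investigational site beyond 48 hours".

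**Step 3. Effect on one arm.** Let f be the afebrile share and p the share of febrile patients with a Day 1 event.

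- Febrile patients only: S(1) = 1 − p.
- As written: S(1) = 1 − p(1 − f).
- All factors from Day 2 on are identical, so the not-resolved curve is multiplied throughout by (1 − p(1 − f))/(1 − p).
- The error in the percentage resolved is f·p·g(t), where g(t) is the share still not resolved at t among those not resolved on Day 1. It falls as g(t) falls.

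The documents give neither f nor p. Over an assumed range the factor is:

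| f | p = 0 | p = 5% | p = 10% | p = 20% | p = 30% |
|---|---|---|---|---|---|
| 30% | 1.00 | 1.02 | 1.03 | 1.08 | 1.13 |
| 50% | 1.00 | 1.03 | 1.06 | 1.13 | 1.21 |
| 70% | 1.00 | 1.04 | 1.08 | 1.18 | 1.30 |

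For f = 50% and p = 10%: (1 − 0.05)/0.90 = 1.056. The shown median is then the time at which the febrile patients' own curve reaches 0.50/1.056 = 47% not resolved, which is later than their median.

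**Step 4. Illustration.** One arm of 160 (the size in SAP 1.3), 80 afebrile, 8 of the 80 febrile patients with a Day 1 event, and later events simulated at a constant rate of 0.15 per day. Day 1 as written: 8/160 = 5.0%. Febrile only: 8/80 = 10.0%.

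| Day | Resolved, febrile only | Resolved, as written | Gap (points) |
|---|---|---|---|
| 1 | 10.0% | 5.0% | 5.0 |
| 4 | 42.5% | 39.3% | 3.2 |
| 7 | 67.5% | 65.7% | 1.8 |
| 15 | 87.5% | 86.8% | 0.7 |
| 29 | 98.8% | 98.7% | 0.1 |

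With no Day 1 event the two curves agree on every day.

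**Step 5. Difference between arms.** With the same f in both arms, shown minus true difference = f(p₀g₀ − p₁g₁), where 1 is sarilumab and 0 is placebo. Assume f = 50%, p₁ = 30%, p₀ = 15%, and 60% versus 39% resolved by Day 3 in febrile patients. The factors are 0.85/0.70 = 1.214 and 0.925/0.85 = 1.088. At Day 3 the shown values are 1 − 0.40 × 1.214 = 51.4% and 1 − 0.61 × 1.088 = 33.6%. Carrying both arms forward at constant daily rates gives:

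| Day | True difference | Shown difference |
|---|---|---|
| 3 | 21.0 | 17.8 |
| 7 | 18.35 | 18.33 |
| 8 | 16.7 | 17.0 |

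The shown difference is too small early and slightly too large from Day 8.

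**Step 6. Test and hazard ratio.** Single simulated data sets with 80 versus 40 febrile patients, without and then with 80 and 40 afebrile patients added, gave these unstratified log-rank z values:

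| Day 1 events, sarilumab / placebo | Febrile only | As written |
|---|---|---|
| 0 / 0 | 1.428 | 1.428 |
| 10% / 5% | 2.347 | 2.343 |
| 20% / 10% | 2.454 | 2.435 |

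In a separate simulation of 90,000 patients the hazard ratio changed by 0.01 or less.

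**The case against.** The strongest reply is that the documents do not establish that any event will be dated Day 1. Resolution needs two consecutive qualifying days, and dating at completion makes the bias exactly zero. Even with first-day dating the conditions are strict:

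- The daily value is the day's maximum, so the four readings taken on Day 1 (Protocol Table 5) make a Day 1 resolution harder.
- On the oral scale fever is above 38.0°C and resolution is 37.2°C or below, a gap of 0.8°C, and the patient must be off antipyretics.
- If pre-dose readings count towards the Day 1 maximum, anyone febrile that morning cannot resolve that day.

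Further, Day 1 censoring already removes afebrile patients from every later risk set, baseline fever is tabulated by arm anyway (SAP 2.1.1), and endpoint #3 is outside the testing hierarchy (SAP 2.4.4.3).

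Most of this stands. It makes the effect conditional, and the values of p used above have no source in the documents. It does not remove the point. Dating by first occurrence leans towards the first day of the run without settling it, and a patient febrile only on the day before dosing meets every condition. The censoring rule is harmless under one reading of the SAP and gives wrong percentages under the other.

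**Conclusion.** The point holds in conditional form, as a minor one. If any resolution is dated Day 1, the Kaplan-Meier percentages resolved for #3 can come out too low and the median too late. For an assumed f = 50% and p = 10% the error is 5 points on Day 1 and below 1 point by Day 15. If no event is dated Day 1, the only consequence is a starting number at risk that includes patients who cannot contribute.

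A reader might infer three stronger things that the documents do not support:

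- **That the percentages will be too low.** This needs a Day 1 event, and the event-dating rule is open.
- **That the difference between arms always shrinks.** It is distorted: smaller early and possibly larger later, as Step 5 shows.
- **That the test is compromised.** The log-rank statistic and hazard ratio are almost unchanged.

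The sizes rest on assumed values of f, p and the later event rates, and on counting patients censored at time 1 as at risk at time 1.

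**What to change.** Replace the censoring sentence in SAP 2.4.4.2 with a restriction: run #3 (log-rank, Cox, Kaplan-Meier and median) in mITT patients with fever at baseline, and show their number per arm. Add which day of the two-day run is the event date.

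The restriction gives the same results as now if there are no Day 1 events, and correct percentages for febrile patients if there are. The cost is a short SAP edit. The displayed number for #3 becomes the febrile patients only.
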